
 
Cerus Endovascular
	
Document Number DNQS428-01
	
Rev. F
	
Page 33 of 119

Clinical Investigation Plan
	
Title
		

Confidential & Proprietary
	
Coil Assisted Flow Diversion: A prospective, single arm, multi-center study to assess the safety and performance of Neqstent in adjunctive therapy (CAFI Study)
		

All patients must sign a study-specific consent form prior to the commencement of any protocol-specific assessments and/or procedures. Final qualification will occur during the implant procedure due to the need for confirmation of IA appropriateness with cerebral angiography.

The patient is enrolled at the time of consent and is considered a study subject in the reporting analysis group only when the patient is fully qualified and at least one Neqstent device has been placed into the patient's body. The following listing provides examples of patient enrollment scenarios for the study:

- The patient is not considered enrolled but not included in the primary analysis group in the study: if at the onset of the procedure in the initial DSA, the investigator determined the patient's IA was not suitable for treatment with the device, thus, no attempt was made by the investigator to place the device. The patient will be treated outside of the study per the investigator's usual practices. The reason for not treating the patient must be documented on a study exit form. The patient is not included in the primary analysis group because the Neqstent was never opened or deployed inside the patient. All patients will be listed in the final report.
- The patient is considered enrolled but not included in the primary analysis group in the study: at the onset of the procedure, the investigator determined the subject's IA was suitable for treatment with the device. The investigator attempted but was unable to place the device within the IA and the subject required alternative treatment. The subject is considered enrolled for the purposes of the study but will only be followed through the 1-month visit. All failed implant attempts will be reported in the final report.

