- The patient is considered enrolled and included in the primary analysis group in the study: if at the onset of the procedure, the investigator determined the subject's IA was suitable for treatment with the device. The investigator successfully placed the device within the IA. The subject is considered enrolled for the purposes of the study and will be followed for the duration of the study.
- The patient is considered enrolled and included in the primary analysis group in the study: if at the onset of the procedure, the investigator determined the subject's IA was suitable for treatment with the device. The investigator successfully placed the device within the IA. In addition, the subject required and received further treatment with another endovascular device(s). The subject is considered enrolled for the purposes of the study and will be followed for the duration of the study.

The available sizes of the Neqstent implant along with coordinating aneurysm dimensions and definitions are provided in Table 7.

 Cerus Endovascular	Document Number DNQS428-01	Rev. F	Page 34 of 119
Clinical Investigation Plan	Title		
Confidential & Proprietary	Coil Assisted Flow Diversion: A prospective, single arm, multi-center study to assess the safety and performance of Neqstent in adjunctive therapy (CAFI Study)		

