## 10.2 Patient Population

Two patient populations will be considered in the analyses, an Intent-to-Treat (ITT) population and a Per Protocol population (PP). The ITT population includes all patients. The PP population will include subjects who complete 6 months of follow-up, die prior to their 6-month clinic visit, or are study failure (withdrawal from study to obtain alternate treatment). The PP will exclude patients with any major protocol violation that affects proper study inclusion or significant outcomes. Endpoints will be evaluated in the PP and ITT populations.

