### Analysis Population

The safety population consists of all patients who are implanted with the study device. The primary analysis for all safety endpoints will be performed on this population.

The analysis for all primary and secondary study endpoints and baseline, procedural and follow-up characteristics will be performed on an intent-to-treat analysis population which will include all available data for all enrolled subjects. Standard summary statistics will be calculated for all study variables.

 Cerus Endovascular	Document Number DNQS428-01	Rev. F	Page 46 of 119
Clinical Investigation Plan	Title		
Confidential & Proprietary	Coil Assisted Flow Diversion: A prospective, single arm, multi-center study to assess the safety and performance of Neqstent in adjunctive therapy (CAFI Study)		

The primary safety endpoint will be calculated as the proportion of subjects with death of any nonaccidental cause or any major stroke within the first 30 days after treatment or major stroke or death due to neurological cause from day 31 to 6 months after treatment.

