#### **Endpoint Analysis:**

The primary performance endpoint will be calculated as the proportion of subjects with complete occlusion demonstrated with a Grade 1 on the Raymond Roy Scale at 6 months follow-up. In the event of a Grade 2 or more using the Raymond Roy Scale, a second assessment will be made at 12- month follow-up to re-assess for complete occlusion and will be reported as a secondary efficacy.

For AE reporting, both subject counts and event counts will be presented in tabular summaries of results.

A summary of subjects with protocol deviations will be reported but those subjects will be included in all analyses although endpoints may be summarized without the subjects (per-protocol analysis group) to provide additional information but not for the primary analysis.

For continuous variables, statistics will include means, standard deviations, medians and ranges. Categorical variables will be summarized in frequency distributions. Missing data will not be imputed. The number of data values available for each analysis will be reported so that the impact of missing data can be seen.

Statistical analyses will be conducted in SAS version 9.4 or above (SAS Institute, Cary, N.C.).

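### The available-case rule for the 6-month occlusion rate drops early deaths and withdrawals for alternate treatment from the denominator and scores retreated aneurysms as graded, so the reported rate tends to run high

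*Combined protocol and SAP*

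**What the plan says.** Section 10.4.1 defines performance success as Raymond Roy Grade 1 on the 6-month angiogram, read by the core laboratory. Section 10.6 (Endpoint Analysis) turns this into a proportion of subjects.

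Section 10.6 (Analysis Population) assigns all primary and secondary endpoints to an "intent-to-treat analysis population which will include all available data for all enrolled subjects". On missing values, Endpoint Analysis says: "Missing data will not be imputed. The number of data values available for each analysis will be reported", with the stated aim of letting the reader see the impact of what is missing. It also says that a per-protocol summary is additional and not for the primary analysis.

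Section 10.2 says: "The ITT population includes all patients". Its per-protocol set keeps subjects who complete 6 months and also those who "die prior to their 6-month clinic visit, or are study failure (withdrawal from study to obtain alternate treatment". No occlusion outcome is attached to either of the latter groups.

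Section 7.5 says: "The patient is enrolled at the time of consent", yet the patient is "considered a study subject in the reporting analysis group only when the patient is fully qualified" and a device has been placed. For a failed implant attempt it says: "The subject is considered enrolled for the purposes of the study but will only be followed through the 1-month visit", and places that subject outside the primary analysis group. Subjects with successful placement are inside the group, including those who also received another endovascular device.

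**The concern.** The study is descriptive (Sections 10 and 10.1). The 6-month occlusion rate is one of its main products and will be judged clinically, so what stands in its denominator matters even without a test.

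An available-case rate treats every subject without a 6-month angiogram as if the reason were unrelated to outcome. That is doubtful for a subject who dies early, and hard to defend for one who leaves to be treated another way, since the plan's own word for that subject is failure. Dropping such subjects raises the rate. Reporting the number of available values shows how many are missing, but not whether they were failures.

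Retreatment acts through a different route. Read literally, the endpoint is the grade on the 6-month angiogram. A target aneurysm that was retreated and then imaged as Grade 1 would count as a success of the initial treatment.

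The sets also do not match: the ITT set of Section 10.6 is all enrolled subjects, with enrollment at consent, while the primary analysis group of Section 7.5 is implanted subjects.

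**Working it through.** **The plan's own figures.** Inputs from Section 10.6: 70% and 55% success, margin 10 points, one-sided 5%, power 80%, attrition 10%. The formula for one arm of a two-arm non-inferiority comparison reproduces the stated number:

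n = (1.645 + 0.842)² × (0.70×0.30 + 0.55×0.45) / (0.70 − 0.55 + 0.10)² = 6.185 × 0.4575 / 0.0625 ≈ 45.3, rounded up to 46.

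46 × 1.10 = 50.6, rounded to 51 (46/0.90 = 51.1 is close). The plan therefore expects 51 − 46 = 5 subjects without 6-month data. Section 11.3 says withdrawals are not replaced.

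**Illustrative scenario.** Assume 51 implanted, 5 without the angiogram, and 70% Grade 1 among those imaged: 0.70 × 46 = 32.2, taken as 32. The 70% is an assumption here, because Section 10.6 ties it to a composite of the primary endpoint components. Intervals are two-sided 95% Clopper-Pearson.

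| Treatment of the 5 not imaged | Rate | 95% CI |
|---|---|---|
| All dropped (available-case) | 32/46 = 69.6% | 54.2 to 82.3 |
| 1 counted as failure, 4 dropped | 32/47 = 68.1% | 52.9 to 80.9 |
| 2 counted as failure, 3 dropped | 32/48 = 66.7% | 51.6 to 79.6 |
| All 5 counted as failure | 32/51 = 62.7% | 48.1 to 75.9 |
| All 5 counted as success | 37/51 = 72.5% | 58.3 to 84.1 |

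One outcome-related exit moves the rate by 1.5 points. The largest possible gap is 6.8 points (69.57 − 62.75).

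**Range over the assumed Grade 1 rate.** With 23 of 46 (50.0%): 23/47 = 48.9% and 23/51 = 45.1%, so 1.1 points for one exit and 4.9 for all five. With 41 of 46 (89.1%): 41/47 = 87.2% and 41/51 = 80.4%, so 1.9 and 8.7 points.

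**Retreatment.** Each subject imaged as Grade 1 after retreatment and rescored as non-success lowers the rate by 1/46 = 2.2 points (31/46 = 67.4%). The documents give no expected number of retreatments.

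**Mismatch of sets.** Suppose 3 of 51 enrolled subjects are failed attempts, 48 are implanted, 43 are imaged and 30 are Grade 1. On available data the rate is 30/43 = 69.8% whichever set is named, because failed attempts are followed for 1 month only and have no 6-month study angiogram. If subjects who were not imaged stay in the denominator, the rate is 30/48 = 62.5% for the implanted set and 30/51 = 58.8% for the enrolled set. The mismatch matters only in that second case.

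**The case against.** The strongest reply is that the plan has already chosen. All available data, no imputation and a per-protocol set that is not primary amount to a prespecified available-case analysis. That stands. A reader might infer from the differing population definitions that the denominator is left open, but the documents do not support this. Section 10.2 keeps deaths and study failures in the per-protocol set, but that is membership of a supplementary set and not a scoring rule. The differing definitions barely touch the rate under the available-case rule, as shown above.

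Second, early deaths are not hidden. Non-accidental death within 30 days and neurological death to 6 months are failures on the primary safety endpoint (Section 10.4.1). Whether they should also be occlusion failures is a choice of estimand, so the point should not rest on a cause-of-death rule. Withdrawal reasons (Sections 7.10 and 7.12) and failed attempts (Section 7.5) are also documented.

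Third, the effect is small: about 1.5 points per exit against an interval about 28 points wide (82.3 − 54.2). Section 7.9 expects few neurologic changes, and Section 10.6 describes the attrition allowance as loss to follow-up, which is mostly not failure. This is why the point is minor.

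What survives is that the chosen rule removes subjects whom the plan itself calls failures, and that the number of available values alone cannot show this.

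**Conclusion.** The concern holds as a minor one. Followed as written, Section 10.6 gives an available-case occlusion rate that is biased upward to the extent that exits before the angiogram are failures. The size is about 1.5 points per such exit if 32 of 46 imaged subjects are Grade 1, and 1.1 to 1.9 points if the Grade 1 rate among those imaged lies between about 50% and 90%. These figures assume 51 implanted and 5 not imaged; the actual reasons for missing angiograms are unknown.

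The 6.8-point gap should not be read as the expected bias. It requires all five losses to be failures, and if all five were successes the available-case rate would be too low instead (69.6% against 72.5%). A reader might also infer that the choice of denominator could reverse a comparison with the 55% quoted for standard treatment. The documents do not support that: Section 10 says the study is not powered for statistical significance, and the plan specifies no test.

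**What to change.** In Sections 10.2 and 10.6 (Analysis Population and Endpoint Analysis):

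- Name the implanted primary analysis group of Section 7.5 as the set for the performance endpoint.
- Count as non-success any subject in that set who, before the 6-month angiogram, withdrew to obtain alternate treatment or had the target aneurysm retreated.
- Leave other missing angiograms, including those due to death, out of the primary rate and report them by reason.
- Add a sensitivity analysis with every implanted subject in the denominator and all missing angiograms counted as failure, and a further line that adds failed implant attempts as failures.

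The cost is wording and minor programming. Withdrawal reasons and failed attempts are already recorded, and Section 9.1 already has deaths adjudicated. One case report form field for target-aneurysm retreatment may be needed; this cannot be checked, because the forms in Appendix F are not in the text available. The headline rate may be somewhat lower.

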## **11 Additional Trial Characteristics**

### **11.1 Measures Taken to Avoid Bias**

The study has been designed to ensure treatment and follow-up of subjects are consistent with current medical practice.

The study will be approved by the central Ethics Committees (ECs) prior to initiation and will undergo continuing review by the ECs as the study progresses. Additionally, each clinical site will provide further oversight and approval of the study.

All investigators must disclose potential conflicts of interest, including financial interests, to the study sponsor prior to participation in the study.

Data from all investigative sites will be monitored throughout the study.

A CEC/DSMB will adjudicate all neurological, device related and procedure related serious adverse events.

A CEC/DSMB will regularly review the study data to provide oversight and necessary input for any trial modifications.

Imaging obtained during the procedure and follow-up period will be reviewed by an independent core laboratory to verify the status of the Neqstent implant and the surrounding vasculature.

 Cerus Endovascular	Document Number DNQS428-01	Rev. F	Page 47 of 119
Clinical Investigation Plan	Title		
Confidential & Proprietary	Coil Assisted Flow Diversion: A prospective, single arm, multi-center study to assess the safety and performance of Neqstent in adjunctive therapy (CAFI Study)		

## 11.2 Special Equipment for Investigation

Apart from the study device, all equipment used in the trial will be maintained and calibrated in accordance with the clinical site institution's policies and procedures.

## 11.3 Procedure for Replacing Withdrawn Subjects

Subjects who withdraw from the study shall not be replaced.

## 11.4 Other Devices Used During Study

Several devices are standardly used during endovascular procedures to treat IAs. Other than the investigational implant and implant delivery system, no special devices are required for this study.

## 11.5 Total Expected Trial Duration

It is expected that the study will take 6 months to enroll a minimum of 51 patients. Follow-ups for the primary endpoint are the 6-month visit and 12-month visit, depending on the Raymond Roy score at the 6-month visit. Total duration of enrollment (6 months), follow-up duration for primary endpoint (6-12 months), 24 months follow-up and reporting (3 months) will take approximately 33 months.

Any patient who is consented but has no implant attempt will be study exited.

All patients must be consented prior to performing study related procedures. All patients that provide consent and are implanted will be followed according to the follow-up schedule. Any patient for whom a failed implant attempt is performed will be followed for 1-month or until resolution of any potential device or implanted related adverse events, whichever occurs last.

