Study Size and Duration	
Study Size: The study population will include 51 subjects enrolled and implanted at up to 11 centers.
 
Study Duration: It is expected that the study will take 6 months to enroll a minimum of 51 patients. Follow-ups for the primary endpoint are the 6-month visit and 12-month visit, depending on the Raymond Roy score at the 6-month visit. Total duration of enrollment approximately 6 months, follow-up duration for primary endpoint (6-12 months), 24 months follow-up and reporting (3 months) will take approximately 33 months.
 
Any patient for whom a failed implant attempt is performed will be followed for 1 month, or until resolution of any potential device or implanted related adverse events, whichever occurs last.
 
Any patient who is consented but has no implant attempt will be study exited.

Device Description	
The Neqstent device works by providing a physical barrier between the parent vessel and the intracranial aneurysm neck (as demonstrated by the Neqstent clinical investigations as well as the pre-clinical research) thereby excluding the aneurysm from the parent artery blood flow. The Neqstent implant is sized to provide a proper fit and position across the neck of the aneurysm. Therefore, blood flow is diverted away from entering at the neck, leading to reduction in flow into the aneurysm cavity with subsequent stasis followed by the formation of thrombus within the confines of the aneurysm. As wound healing progresses and fibrosis occurs over the ensuing days and months, it serves to strengthen the physical barrier between the parent vessel and the aneurysm cavity. The weakened vascular tissue of the aneurysm cavity, in particular the dome, is thus protected from the shear wall stresses generated by the previous blood flow.
  
Figure 1 - Neqstent
 
The Neqstent (NQS) (NQS407-XX, NQS409-XX, NQS411-XX) is an intrasacular, self-expanding, embolization device intended for the treatment of intracranial aneurysms. The NQS is shown in Figure 1 and comprises an:
 
Implant
 
The implant is a self-expanding concave shaped device comprised of a double layer nickel-titanium and platinum wire mesh, and a platinum marker. The implant is packaged unconstrained in a protective dispenser hoop with an Introducer preloaded onto the DPW shaft just proximal to the implant.

Clinical Investigation Plan

Title

*Confidential & Proprietary*

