**Table 1. Implant Size Selection Guide**

REF (Catalog Number) – Diameter	Aneurysm Neck (mm)
NQS407-XX – 7 mm	3.0 - 5.0
NQS409-XX – 9 mm	4.0 - 6.0
NQS411-XX – 11 mm	5.0 - 8.0

 Stryker Neurovascular Excelsior® XT-27® (0.027" ID, 2.9F/2.7F OD, 150cm Length)

 Detachable Coil Power Supply: Stryker Neurovascular InZone® Detachment System, REF M00345100940

 Power Supply Detachment Cable: Stryker Neurovascular IZDS Connecting Cable, REF 00345110250

Clinical Investigation Plan

Title

*Confidential & Proprietary*

**Coil Assisted Flow Diversion: A prospective, single arm, multi-center study to assess the safety and performance of Neqstent in adjunctive therapy (CAFI Study)**

Objective and Endpoints	
The primary objective of this study is to document the safety and performance of the Neqstent.
 
1. Primary Safety Endpoint:
 
The proportion of subjects with death of any non-accidental cause or any major disabling stroke within the first 30 days after treatment or major disabling stroke or death due to neurological cause from day 31 to 6 months after treatment.
 
Note: Major Disabling Stroke is defined as an episode of neurological signs or symptoms that persist beyond 24 hours accompanied with evidence of ischemia/infarction on imaging that results in an increase of NIHSS from baseline by <math>\geq 4</math> points and/or an increase from mRS baseline by <math>>2</math>.
 
2. Primary Performance Endpoint:
 
To demonstrate the occlusion rate on the 6 month angiogram as adjudicated by a core laboratory. Success will be defined as complete occlusion demonstrated by a Grade 1 using the Raymond Roy Scale.
 
Note: In the event of a Grade 2 or more using the Raymond Roy Scale, a second assessment will be made at 12 month follow-up to re-assess for remnant stability and/or complete occlusion and will be reported as a secondary efficacy endpoint.

Sample Size	51 subjects will be enrolled to obtain adequate follow-up data for the study to complete sponsor obligation to the notified body.
Number of Sites	Up to 11 sites will enroll in the study.
Study Visits	Baseline, procedure, discharge, one (1) month, six (6) months, twelve (12) months and twenty-four (24) months.

Clinical Investigation Plan

Title

*Confidential & Proprietary*

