### 10.1 Justification of Methodology

This study is designed as a single arm, descriptive study to develop further understanding of the Neqstent. It will provide safety and performance information for subjects from the Neqstent implantation to 24-month follow-up.

At one -month post procedure, the subjects will provide an adverse event profile related to the placement of the device. At six months of the study there will be additional information related to the adverse event profile including any device related instability or deficiency.

Similarly, the subjects will provide a performance profile. At six months post procedure, the information will provide how well the aneurysm has healed or embolized through the analysis of imaging performed by the independent core lab for accuracy and removal of bias. Note: In the

 Cerus Endovascular	Document Number DNQS428-01	Rev. F	Page 44 of 119
Clinical Investigation Plan	Title		
Confidential & Proprietary	Coil Assisted Flow Diversion: A prospective, single arm, multi-center study to assess the safety and performance of Neqstent in adjunctive therapy (CAFI Study)		

event of a Grade 2 or more using the Raymond Roy Scale, a second assessment will be made at 12- month follow-up to re-assess for complete occlusion and will be reported as a secondary efficacy.

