## 10.4 Endpoints

### 10.4.1 Primary Endpoints

#### **Primary Safety Endpoint:**

The proportion of subjects with death of any non-accidental cause or any major disabling stroke within the first 30 days after treatment or major disabling stroke or death due to neurological cause from day 31 to 6 months after treatment.

Note: Major Disabling Stroke is defined as an episode of neurological signs or symptoms that persist beyond 24 hours accompanied with evidence of ischemia/infarction on imaging that results in an increase of NIHSS from baseline by  $\geq 4$  points and/or an increase from mRS baseline by  $>2$ .

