#### **Primary Performance Endpoint:**

To demonstrate the occlusion rate on the 6 month angiogram as adjudicated by a core laboratory. Success will be defined as complete occlusion demonstrated by a Grade 1 using the Raymond Roy Scale.

Note: In the event of a Grade 2 or more using the Raymond Roy Scale, a second assessment will be made at 12 month follow-up to re-assess for remnant stability or complete occlusion and will be reported as a secondary efficacy endpoint.

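### Does the trial-duration text move the primary endpoint from 6 months to 6-12 months?

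*Combined protocol and SAP*

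**What the plan says.** Two timeline paragraphs, Study Size and Duration in the synopsis (Section 2) and Section 11.5, carry the same sentence: "Follow-ups for the primary endpoint are the 6-month visit and 12-month visit, depending on the Raymond Roy score at the 6-month visit". Each then lists the "follow-up duration for primary endpoint (6-12 months") and closes the sum with "24 months follow-up and reporting (3 months) will take approximately 33 months".

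The endpoint text reads differently:

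- **Primary performance** (synopsis, Objective and Endpoints; Section 10.4.1): "To demonstrate the occlusion rate on the 6 month angiogram as adjudicated by a core laboratory", with success meaning Grade 1.
- **Calculation** (Section 10.6, Endpoint Analysis): the proportion of subjects with "complete occlusion demonstrated with a Grade 1 on the Raymond Roy Scale at 6 months follow-up".
- **Primary safety** (synopsis; Section 10.4.1): the second and last part of the window is "major disabling stroke or death due to neurological cause from day 31 to 6 months after treatment". The safety paragraph in Section 10.6 has the same 6-month limit.
- **12-month look in patients at Grade 2 or more**: Section 10.4.1 uses it to "re-assess for remnant stability or complete occlusion and will be reported as a secondary efficacy endpoint". Section 10.1 uses it to "re-assess for complete occlusion and will be reported as a secondary efficacy", and the footnotes to Tables 2 and 8 give it the same secondary status.

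**The concern.** A reader who starts with the synopsis is told that the 12-month visit belongs to the primary endpoint for some patients. A few lines later the same synopsis calls that visit secondary. No sentence says which part of the document prevails.

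The ambiguity also has a direction. Under Section 7.9 only aneurysms at Grade 2 or more at 6 months have a scheduled 12-month angiogram. A rate of Grade 1 by 6 or 12 months could therefore add successes in the same patients and never remove one. An aneurysm that was Grade 1 at 6 months and later reopened would have no scheduled 12-month angiogram to show it. Reopening is not a remote event: Table 5 puts recanalization at 5-15%, and Section 4 cites a multicentre cohort with another intrasaccular device in which complete occlusion was 67% in the short term and 58% in the long term.

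At stake would be a flattering primary rate and a later date for complete primary data.

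**Working it through.** **1. The plan's duration.** Section 11.5 gives enrolment 6 months, follow-up 24 months and reporting 3 months.

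6 + 24 + 3 = 33 months, as stated.

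Adding the 6-12 months as a separate block would give 39 to 45. The phrase therefore describes a stretch inside the 24 months and does no work in the sum.

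**2. The plan's sample size.** Section 10.6 gives 70% for the device, 55% for standard treatment, a margin of 10%, one-sided 5% and 80% power. The two-proportion non-inferiority formula gives:

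n = (1.645 + 0.842)² × (0.55 × 0.45 + 0.70 × 0.30) / (0.70 − 0.55 + 0.10)² = 6.185 × 0.4575 / 0.0625 = 45.3, rounded up to 46.

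46 × 1.10 = 50.6, rounded up to 51.

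Both stated figures reproduce. Whether that formula suits a single arm is a separate question. No visit time enters it, and Section 10.6 ties the 46 to 6-month data.

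**3. Which text can be executed.** The Endpoint Analysis text gives an analyst a numerator (Grade 1), a scale (Raymond Roy) and a time (6 months), and assigns the 12-month result to secondary reporting. The duration text names visits only. It does not say how results from two visits would be combined, so a 6-or-12-month rate would need a rule found nowhere in the document. Nor can the sentence describe the safety endpoint, because it depends on an angiographic grade.

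**4. Size if the rule were ignored.** Let p be the 6-month Grade 1 rate and c the share of failures reaching Grade 1 by 12 months. Both are assumed: the documents give no conversion rate, and the 70% in Section 10.6 is stated for a composite. The rate becomes p + (1 − p)c.

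| p | c = 10% | c = 20% | c = 30% |
|---|---|---|---|
| 60% | 64% | 68% | 72% |
| 70% | 73% | 76% | 79% |
| 80% | 82% | 84% | 86% |

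The gain is 2 to 12 points. In 46 patients at 70%, about 32 are Grade 1 and 14 are re-imaged. The expected conversions are 1.4, 2.8 and 4.2. Rounded to 1, 3 and 4, they give 33/46 (71.7%), 35/46 (76.1%) and 36/46 (78.3%).

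The plan has no pass mark. Under an assumed exact one-sided 5% rule against 55% (at least 32 of 46), the chance of passing at a true 6-month rate of 55% would rise from 3.2% to 10.6%, 26.7% or 50.9% for c = 10%, 20% or 30%.

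**5. Timing.** With 6 months of enrolment, and before the one-month visit window, the last primary visit falls at 6 + 6 = month 12 under the definitions and 6 + 12 = month 18 under the duration text. No stated action hangs on that date. The interim summary follows 10 enrolled patients (Section 10.5), the DSMB reviews after five patients and then about twice a year (Section 9.2), and the final report waits until the data requirements are met (Section 12.1.15).

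**The case for a change.** The strongest argument for a change is that the slip concerns the primary time point and sits in the synopsis. It also has some support inside the statistical section: the opening of Section 10.6 expects 51 patients with evaluable data at 6 months and, if needed, at 12. Anyone wishing to count late conversions could cite that clause together with the two duration paragraphs, and no sentence expressly bars adding them. Correcting it would cost a few words.

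The inconsistency itself stands, and so does the one-way direction of any error. The claim that the analysis is left open does not. The clause in Section 10.6 says which data are expected, not which endpoint they feed, and the same section then sizes the study on 6-month data. An express bar is unnecessary when the primary numerator is already defined at 6 months and the 12-month result already has a different label. The pass probabilities are illustrative at most, because Section 10 says the study is not powered for a significance test and Section 10.1 calls it descriptive.

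**Conclusion.** This is a clerical slip in the timeline text, and no change to the plan is needed. Applied as written, the plan gives a 6-month primary performance rate, a 6-month primary safety rate and a separate secondary 12-month result. The primary rate, the 46 and 51 subjects, the visits and the 33 months are unaffected.

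The 2 to 12 point inflation arises only with assumed 6-month rates of 60-80%, assumed conversion of 10-30%, and an analyst who sets aside the explicit calculation in Section 10.6. The conclusion rests on that calculation governing the analysis, which the synopsis endpoint text, Sections 10.1 and 10.4.1 and, for the imaging, the schedule footnotes all support. If the document is revised for other reasons, the duration wording can be tidied then, with no effect on any result.
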